5.5.2 Key secondary analysis

5.5.2.1 Secondary analysis for continuous endpoints

For continuous endpoints of change from extension study baseline in UAS7/HSS7/ISS7 score at Week 12, the secondary analysis will be performed based on the data after the missing data imputation for the intercurrent events have been performed.

The SAS procedure `proc mi` will be used for multiple imputation. Sample code refer to Section 5.5.1.

The SAS procedure `proc means` will be used to calculate the group means for each imputed dataset with the following sample code:

```
proc means data = ...;  
by _imputation_ group notsorted;  
var wk12cfb;  
Output out = sumstat mean = meancfb std = stdcfb;  
run;  
where _imputation_ = the index for imputation times  
    group = treatment group  
    wk12cfb = change from baseline UAS7/HSS7/ISS7 score at Week 12 in TRT1  
    sumstat is the dataset which includes the mean estimate (meancfb) and the standard error (stdcfb) in each group.
```

The SAS procedure `proc mianalyze` will be used to combine the parameter estimates across imputed datasets with the following sample code:

```
ods output ParameterEstimates = pe_comb;  
proc mianalyze data = sumstat;  
by group;  
ModelEffects meancfb;  
stderr stdcfb;  
run;
```

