The absolute change from extension study baseline in UAS7 score at Week 12 will be summarized descriptively, it will be provided together with 95% confidence interval. The change from extension study in UAS7 components (ISS7 and HSS7) will also be provided in descriptive manner at Week 12.

Similar missing data imputation rules as the primary endpoint analysis based on change from baseline in UAS7 score at week 12 will be used for this secondary endpoint analyses. The imputations for ISS7 and HSS7 will follow the same missing data imputation rules.

- Percentage of subjects achieving DLQI = 0-1 (no impact on subjects QoL) at Week 12 after retreatment of ligelizumab for subjects receiving the same dose regimen as in the core studies.

An overall score will be calculated according to the scoring manual. The proportion of subjects with overall DLQI scores ≤ 1 at Week 12 will be summarized in a descriptive manner, it will be provided together with a 95% Clopper-Pearson exact confidence interval. Similar missing data imputation rules as the primary endpoint analysis will be applied in this secondary efficacy endpoint analysis. The missing data imputation will be based on the proportion of subject with UAS7 = 0 at week 12.

- Cumulative number of weeks that subjects achieve AAS7 = 0 between extension study baseline and Week 12

The cumulative number of weeks achieving AAS7 = 0 response between baseline and Week 12 will be derived based on the AAS eDiary. A weekly AAS7 score will be derived by adding up the daily scores of the 7 days preceding the visit, and ranges from 0 to 105. For a weekly AAS7 score, if one or more of the daily scores are missing, the same principles as handling the weekly score from UPDD will be applied to handle the missing data. If the AAS7 score is missing, similar missing imputation rules as the primary analysis will be applied on AAS7 = 0 proportion over the first 12 weeks. The imputed AAS7 = 0 will be used for the cumulative number of weeks that subjects achieve AAS7 = 0 response calculation. The cumulative frequency plot will be provided together with the summary statistics.

- Percentage of subjects achieving UAS7 ≤ 6 (well-controlled urticaria) at 12 weeks after starting self-administration in the first half of the treatment period.

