5.5 Statistical models and SAS sample code

5.5.1 Primary analysis

The primary analysis will be performed based on the data after the missing data imputation for the intercurrent events has been performed.

Step 1:

The SAS procedure `proc mi` will be used for multiple imputation for change from baseline in UAS7 score with the following sample code:

```
proc mi data=... out=... nimpute=... seed=123;  
by group;  
class ige cuind group;  
fcs reg(/details);  
var ige cuind group baseline wk12cfb;  
run;
```

where `group` = treatment group
`ige` = baseline IgE
`cuind` = baseline CU index
`baseline` = baseline UAS7 score
`wk12cfb` = change from baseline UAS7 score at Week 12 in TRT1.

If the imputation model does not converge, remove the covariates as needed until it converges.

The following SAS sample code will be used to transfer the continuous variable change from baseline in UAS7 score to a binary response of $UAS7 \leq 6$, and conduct non-responder imputation for subjects who discontinued due to study early termination:

```
data ...;  
set ...;  
resp = (baseline + wk12cfb) <= 6;  
if flag = 0 then resp = 0;  
run;
```

where `resp` = binary response of $UAS7 \leq 6$
`baseline` = baseline UAS7 score
`wk12cfb` = change from baseline UAS7 score at Week 12 in TRT1
`flag` = flag of missingness
(1 = missing due to study early termination, 0 = missing not due to study early termination, . = data is observed).

Note that the order of multiple imputation and non-responder imputation could be reversed as needed.

Step 2:

The SAS procedure `proc freq` will be performed to calculate the primary endpoint (binary response of $UAS7 \leq 6$ at Week 12) for each imputed dataset with the following sample code:

```
proc freq data = ...;  
by _imputation_group;  
tables resp /nopercnt nocol norow nocum binomial(level = "1" cl =  
wilson(correct));  
output out = sumstat binomial;  
run;
```

where `_imputation_` = the index for imputation times

group = treatment group

resp = binary response of UAS7≤6

sumstat is the dataset which includes the response rate estimate and the standard error in each group

Here “cl = wilson(correct)” is used to calculate the 95% confidence intervals by Wilson score method with continuity correction.

Step 3:

Rubin’s Rule:

Rubin’s Rule will be applied to combine the multiple sets of estimates to produce the overall estimates, standard error, confidence interval and p-values.

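### The pooling code for change from baseline in UAS7, HSS7 and ISS7 passes a standard deviation to Rubin's rules as the standard error, so 95% intervals run as written would be too wide by about √n

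*SAP*

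**What the plan says.** SAP section 5.5.2.1 gives a three-step recipe for change from extension baseline in UAS7, HSS7 and ISS7 at Week 12: impute with PROC MI, summarise each completed dataset by group with PROC MEANS, and pool with PROC MIANALYZE.

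The summary step is "Output out = sumstat mean = meancfb std = stdcfb". The accompanying note says that the output dataset "includes the mean estimate (meancfb) and the standard error (stdcfb) in each group". The pooling step names the estimate with "ModelEffects meancfb" and its standard error with "stderr stdcfb".

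On the reported result, SAP section 2.6.1 states that the UAS7 change will be "summarized descriptively, it will be provided together with 95% confidence interval". For the two components it asks only for a descriptive summary. Table 2-16 keeps all three changes in the final analysis, and the Amendment 3 change log records that the sample code for multiple imputation was added to section 5.5 in that amendment, so this is current text.

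**The concern.** The note and the code disagree. The note calls `stdcfb` a standard error, but the `std=` keyword in PROC MEANS writes the sample standard deviation. No later statement rescales it.

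PROC MIANALYZE squares whatever it is given as `stderr` and averages the squares to form the within-imputation variance. Given a standard deviation, it builds an interval for the spread of individual patients and labels it an interval for the group mean.

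SAP section 2.6.2 plans no inferential methods for the secondary endpoints, so this interval is the main statement of precision for the UAS7 change. A precisely estimated improvement would be reported as highly uncertain, and adding subjects would hardly narrow it.

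**Working it through.** **The plan's own figures.** The documents give no SD, no number of imputations and no result for this endpoint, so there is no stated figure to reproduce. For n, I use SAP Table 3-1: 250, 450 or 600 per group with 10% drop-out, i.e. 0.9 × 250 = 225, 0.9 × 450 = 405, 0.9 × 600 = 540. These are the sizes behind that table: a Wald interval with responders rounded up to a whole number returns its limits (48.6–61.6, 50.2–59.9, 50.8–59.2).

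**Comparison within the SAP.** The other two pooling blocks pass real standard errors: `E_BIN` for the binary response (5.5.1) and `StdErrMu` for the count of angioedema-free weeks (5.5.2.3). Only the continuous block passes an SD.

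**Formulas.** SAP section 5.5.1 says that Rubin's Rule "will be applied to combine the multiple sets of estimates to produce the overall estimates, standard error, confidence interval and p-values". With W the mean squared standard error, B the between-imputation variance and m imputations:

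- total variance T = W + (1 + 1/m)B
- relative increase r = (1 + 1/m)B / W, degrees of freedom (m − 1)(1 + 1/r)²
- half-width = t × √T

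Correctly, W = s²/n. As coded, W = s². Let λ be the share of the correct total variance that comes from imputation. Then the correct T is (s²/n)/(1 − λ), the coded T is s² + (s²/n)·λ/(1 − λ), and

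- (coded T)/(correct T) = n(1 − λ) + λ

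so the interval is too wide by √(n(1 − λ) + λ), apart from a very small difference in the t quantile. At λ = 0 this is exactly √n.

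**Numbers.** Half-widths in UAS7 points use an assumed SD of 12 and λ = 0; ratios use m = 100.

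| n | half-width as coded, 1.96 × 12 | correct half-width, 1.96 × 12/√n | ratio, λ = 0 | ratio, λ = 0.10 | ratio, λ = 0.30 |
|---|---|---|---|---|---|
| 225 | 23.5 | 1.57 | 15.0 | 14.2 | 12.6 |
| 405 | 23.5 | 1.17 | 20.1 | 19.1 | 16.8 |
| 540 | 23.5 | 1.01 | 23.2 | 22.0 | 19.4 |

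For n = 225 and an assumed SD of 8 to 15, the coded half-width is 15.7 to 29.4 against a correct 1.05 to 1.96.

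**Simulation.** Using normal-regression imputation on baseline with 50 imputations and assumed data, the ratios at n = 225, 405 and 540 were 14.2, 19.3 and 22.3 with 10% of values imputed, and 13.5, 17.9 and 20.8 with 20% imputed.

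**Plausibility on the scale.** UAS7 runs from 0 to 42, so the mean improvement cannot exceed 42. If the half-width exceeds 21 (SD above 21/1.96 = 10.7), every possible mean improvement gives an interval that either includes zero or runs past 42. At SD 12 the full interval is about 2 × 23.5 = 47 points wide. At SD 8, mean improvements between 15.7 and 42 − 15.7 = 26.3 points avoid both.

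**Degrees of freedom.** Because W is n times too large, r is n times too small. The fraction of missing information is understated and the t quantile moves towards 1.96. This matters little for the width beside the factor in W.

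**The case against.** The strongest reply is that this is sample code and the text beside it says a standard error is meant. The method is therefore stated correctly, one keyword contradicts it, and a careful programmer would notice. The direction is conservative, point estimates do not change, and no test or decision rests on the interval. The unplanned interim analysis (SAP 2.13.2.4) uses observed data and never reaches this code. For ISS7 and HSS7 the plan promises only a descriptive summary, although the code covers them too.

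Most of this is true and limits the reach of the point. It does not remove it. The SAP is the specification against which programs are checked, and calling an SD a standard error makes the slip harder to see. An interval 12 to 23 times too wide is not usefully conservative, because it no longer describes the precision of the mean.

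Two qualifications on size also stand. The factor is exactly √n only when no variance comes from imputation; otherwise it is about √(n(1 − λ)). And whether the interval would cover zero depends on a mean change and an SD that the documents do not give.

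**Conclusion.** The point holds. If the code in SAP section 5.5.2.1 is run as written, the 95% interval for change in UAS7, and any interval produced for HSS7 and ISS7, is too wide by about √n. At the planning sizes of 225 to 540 per group that means 15.0 to 23.2 times with no imputation variance, and 12.6 to 19.4 times if 30% of the correct variance comes from imputation. The coded half-width stays near 1.96 × SD whatever the sample size.

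The ratios do not depend on the SD. The widths in points rest on an assumed SD of 8 to 15. The n values are planning scenarios: early termination may leave fewer subjects (at n = 50 the factor is still about 7), while imputation may bring the number back towards the full 250, 450 or 600 (15.8, 21.2 and 24.5 times at λ = 0). The documents contain no results, so this is a fault in the specification and not a demonstrated error in a report. It should be corrected before the final analysis is run.

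**What to change.** In SAP section 5.5.2.1, change the PROC MEANS output statement to `output out = sumstat mean = meancfb stderr = secfb;`, change the PROC MIANALYZE statement to `stderr secfb;`, and rename the variable in the explanatory note. Apply the same change for UAS7, HSS7 and ISS7. If the SD is wanted for the descriptive table, output it as a separate variable and do not pool it as a standard error.

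While editing, say in section 2.6.1 whether a 95% interval is also intended for ISS7 and HSS7, since the code would produce one.

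The cost is one keyword and a variable name in the SAP and the program. No data, design feature or other analysis changes.

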5.5.2.2 Secondary analysis for binary endpoints

For binary endpoints of UAS7=0/DLQI 0-1 at Week 12, the secondary analysis will be performed based on the data after the missing data imputation for the intercurrent events has been performed.

The SAS procedure `proc mi` will be used for multiple imputation with the following sample code:

```
proc mi data=... out=... nimpute=... seed=123;  
by group;cuin  
class ige cuind group week12;  
fcs logistic (week12 = ige cuind group baseline / details);  
var ige cuind group baseline week12;  
run;  
where group = treatment group  
    ige = baseline IgE
```

cuind = baseline CU index
baseline = baseline UAS7 score
week12 = binary response of UAS7=0/DLQI 0-1 at Week 12 in TRT1.

If the imputation model does not converge, remove the covariates as needed until it converges.

The SAS procedure `proc freq`, and `proc mianalyze` will be used for the analysis. Sample code refer to Section 5.5.1. Wilson score method is not necessary for 95% confidence limits calculation in secondary analysis. Other methods could be performed as needed.

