12.5 Analysis of secondary endpoints

12.5.1 Efficacy and/or Pharmacodynamic endpoint(s)

- Complete control of urticaria at Week 12 after retreatment of ligelizumab for subjects receiving the same dose regimen as in the core studies, assessed as percentage of subjects achieving $UAS7 = 0$.

The proportion of subjects with $UAS7 = 0$ at Week 12 will be summarized in a descriptive manner, it will be provided together with 95% confidence interval. Missing data will be considered as non-responder in the analysis.

- Absolute change from extension study baseline in $UAS7$ at Week 12 after retreatment of ligelizumab for subjects receiving the same dose regimen as in the core studies.

The absolute change from extension study baseline in $UAS7$ score at Week 12 will be summarized descriptively, it will be provided together with 95% confidence interval. The change from extension study in $UAS7$ components (ISS7 and HSS7) will also be provided in descriptive manner at Week 12.

- No impact on subjects QoL at Week 12 after retreatment of ligelizumab for subjects receiving the same dose regimen as in the core studies, assessed as percentage of subjects achieving $DLQI = 0-1$.

An overall score will be calculated according to the scoring manual. The proportion of subjects with overall $DLQI$ scores ≤ 1 at Week 12 will be summarized in a descriptive

manner, it will be provided together with a 95% confidence interval. Missing data will be considered as non-responder in the analysis.

- Cumulative number of weeks that subjects achieve AAS7 = 0 between extension study baseline and Week 12

The cumulative number of weeks achieving AAS7 = 0 response between baseline and Week 12 will be derived based on the AAS eDiary. A weekly AAS7 score will be derived by adding up the daily scores of the 7 days preceding the visit, and ranges from 0 to 105. For a weekly AAS7 score, if one or more of the daily scores are missing, the same principles as handling the weekly score from UPDD will be applied to handle the missing data. If the AAS7 score is missing, it will be considered as a non-response for the cumulative number of weeks that subjects achieve AAS7 = 0 response calculation. The cumulative frequency plot will be provided together with the summary statistics.

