2.5.3 Handling of missing values/censoring/discontinuations

The UAS7 score is derived from the sum of the HSS7 score and the ISS7 score, as noted above. The HSS7 and ISS7 score will be derived by adding up the daily HSS and ISS scores of the 7 days preceding the visit, respectively. The daily score (HSS and ISS) will be calculated by averaging the morning and evening HSS and ISS score, respectively. If one of the morning or evening scores is missing, the non-missing score for that day (morning or evening) will then be used as the daily score.

A minimum of 4 out of 7 daily scores are needed to reliably calculate a weekly HSS7, ISS7 or UAS7 score. For each weekly score from UPDD (i.e. HSS7, ISS7 and UAS7 score), if one or more of the daily scores are missing, the following principles will be applied to handle the missing data:

- If a subject has at least 4 “non-missing” daily scores within the 7 days prior to the study visit, the weekly score will be calculated as the sum of the available eDiary scores of that week, divided by the number of non-missing days, multiplied by 7.
- If there are less than 4 “non-missing” daily scores within the prior 7 days, then the weekly score will be considered as missing for that week.

Subjects who discontinue from study treatment early will be encouraged to stay in the study following the procedures described in the study protocol Section 9.1.1. These are considered as retrieved dropout (RDO) subjects.

The primary analysis will account for different post-dosing events for missing data handling as follows:

- Discontinuation of initially assigned study treatment prior to Week 12 (Visit 204) due to AEs or lack of efficacy or any other reasons, except for the reason of study early termination: Retrieved dropout (RDO) data collected after study treatment discontinuation will be used for analysis. If no RDO data was collected after study treatment permanent discontinuation, non-responder imputation will be applied for missing data imputation.
- Discontinuation of initially assigned study treatment prior to Week 12 (Visit 204) due to study early termination: the efficacy data collected after the discontinued treatment will be censored. The missing data caused by this intercurrent event occurrence will be imputed based on the treatment arm (ligelizumab 72 mg or 120 mg q4w) data under the missing at random (MAR) assumption using multiple imputation separately.

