2.6.1 Key secondary endpoints

For all secondary efficacy analyses, the FAS (or subpopulations within FAS) will be used. All listings and tables will be presented by treatment group unless stated otherwise. All data will be included in the analysis regardless of rescue medication use.

All secondary analyses to be performed in this study are described and summarized in

Table 2-9.

Table 2-9 Overview of analyses on secondary efficacy endpoints

Analysis Population and Analysis Period/time point	Endpoints and Analysis
Objective: to assess the retreatment efficacy of ligelizumab	

population: Ligelizumab retreatment subpopulation
 
period/time point: TRT1A/Visit204 (Week 12)
	
 • The proportion of subjects with completely controlled urticaria (UAS7 = 0) at Week 12 • Absolute change from extension study baseline in the UAS7 and its components (ISS7 and HSS7) at Week 12 • Cumulative number of weeks that subjects achieve weekly angioedema activity score (AAS7) = 0 between extension study baseline and Week 12 • Percentage of subjects achieving DLQI = 0-1 at Week 12
Objective: to assess the self-administration efficacy	

Population: self-administer subpopulation, who have at least one self-administration in TRT1B
 
Period/time point: 12 weeks after starting outside-clinic self-administration in TRT1B
	
 • The proportion of subjects with well-controlled disease (UAS7 ≤ 6), 12 weeks after starting self-administration

- Percentage of subjects achieving UAS7 = 0 (complete control of urticaria) at week 12 after retreatment of ligelizumab for subjects receiving the same dose regimen as in the core studies.

The proportion of subjects with UAS7 = 0 at Week 12 will be summarized in a descriptive manner, it will be provided together with 95% Clopper-Pearson exact confidence interval.

Similar missing data imputation rules as the primary endpoint analysis will be applied in this secondary efficacy endpoint analysis. The missing data imputation will be based on the proportion of subject with UAS7 = 0 at week 12.

- Absolute change from extension study baseline in UAS7 at Week 12 after retreatment of ligelizumab for subjects receiving the same dose regimen as in the core studies.

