5.5.2.3 Secondary analysis for count endpoint

For count endpoint of cumulative weeks with AAS7=0 up to Week 12, the secondary analysis will be performed based on the data after the missing data imputation for the intercurrent events have been performed.

The SAS procedure `proc mi` will be used for multiple imputation with the following sample code:

```
proc mi data=... out=... nimpute=... seed=123;  
by group;cuin  
class ige cuind group week1-week12;  
fcs logistic (week1-week12 = ige cuind group baseline / details);  
var ige cuind group baseline week1-week12;  
run;
```

where group = treatment group
ige = baseline IgE
cuind = baseline CU index
baseline = baseline UAS7 score
week1-week12 = binary response of AAS7=0 at Week 1-12 in TRT1.

If the imputation model does not converge, remove the covariates as needed until it converges.

The SAS procedure `proc genmod` will be used to calculate the group means for each imputed dataset with the following sample code:

```
ods output LSMeans = sumstat;  
proc genmode data = ... order = internal;  
by _imputation_;  
class group / param = glm;  
model cum = group / noint dist = negbin link = log;  
lsmeans group / cl ilink e;  
run;
```

where _imputation_ = the index for imputation times
group = treatment group
cum = the cumulative weeks of AAS7=0 up to week 12
sumstat is the dataset which includes the mean estimate and the standard error in each group.

The SAS procedure `proc mianalyze` will be used to combine the parameter estimates across imputed datasets with the following sample code:

```
ods output ParameterEstimates = pe_comb;
proc mianalyze data = sumstat;
by group;
ModelEffects Mu;
stderr StdErrMu;
run;
```

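### As printed, the SAP sample code for UAS7 = 0, DLQI 0-1 and weekly AAS7 = 0 has no non-responder step, so literal use would put non-termination drop-outs without retrieved data under MAR, contrary to SAP 2.6.1 and 2.5.3

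*SAP*

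**What the plan says.** **Rule in the SAP text.** For UAS7 = 0, SAP 2.6.1 states: "Similar missing data imputation rules as the primary endpoint analysis will be applied in this secondary efficacy endpoint analysis". It repeats this for DLQI 0-1 and has an equivalent sentence for AAS7 = 0 over the first 12 weeks. The primary rules are in SAP 2.5.3:

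- Data retrieved after discontinuation are used as observed.
- For discontinuation other than through study early termination: "If no RDO data was collected after study treatment permanent discontinuation, non-responder imputation will be applied for missing data imputation".
- MAR multiple imputation is kept for study early termination and, in step 1 of the imputation procedure, for intermittent missing values. The remainder is non-response.

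**Code in the SAP appendix.** For the primary endpoint, 5.5.1 runs PROC MI and then a data step containing "if flag = 0 then resp = 0", where flag 0 marks a value missing for a reason other than study early termination. For UAS7 = 0 and DLQI 0-1, 5.5.2.2 prints PROC MI with "fcs logistic (week12 = ige cuind group baseline / details" and refers back to 5.5.1 only for PROC FREQ and PROC MIANALYZE. For AAS7, 5.5.2.3 prints "fcs logistic (week1-week12 = ige cuind group baseline / details", followed by its own PROC GENMOD and PROC MIANALYZE, with no reference to 5.5.1. Neither subsection has a missing-reason flag or a non-responder statement.

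**Protocol.** Section 12.5.1 counts every missing UAS7 = 0 or DLQI 0-1 value as non-response and says of angioedema: "If the AAS7 score is missing, it will be considered as a non-response".

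**The concern.** Amendment 3 added this sample code for the final analysis, so a programmer is likely to start from it. Followed as printed, it gives a subject who left for lack of efficacy, with no later data, a modelled chance of complete control, of DLQI 0-1 or of an angioedema-free week. The SAP text gives that subject zero. The error can only raise the reported results. The UAS7 = 0 rate would also rest on a different missing-data basis from the UAS7 ≤ 6 rate reported for the same subjects.

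The SAP text does not fully protect against this. It asks only for similar rules. Step 2 of the 2.5.3 procedure confines non-responder imputation to the primary endpoint, and the catch-all sentence in that section names only UAS7, HSS7 and ISS7. For DLQI and AAS7 the programmer therefore has a loosely worded rule and code without the step.

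**Working it through.** The documents state no figure for this point, so there is none to reproduce. The check sets code against text and then sizes the difference.

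**Side by side, for a drop-out not caused by study termination, with no retrieved data:**

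| Source | Week 12 response |
|---|---|
| Protocol 12.5.1 | 0 |
| SAP 2.6.1 with 2.5.3 | 0 |
| SAP 5.5.1 code (primary endpoint) | 0, through the flag |
| SAP 5.5.2.2 and 5.5.2.3 code, run alone | logistic MAR draw |

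**Inputs for size, all illustrative.**
- p = 44.0%, the UAS7 = 0 rate after the third 72 mg dose in the Phase IIb study (Protocol 4.1.1).
- m = share missing at Week 12: 10% (SAP Table 3-1) or 15% (SAP 3.1, responder subgroup), both planning drop-out rates.
- f = share of that missingness that is neither termination-related nor intermittent. The documents give no value, so the range 0 to 1 is shown.

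**Formulas.** The printed code alone gives about p, the SAP 2.6.1 rule gives p(1 − fm), and the overstatement is pfm.

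| m | f | Printed code | SAP 2.6.1 rule | Difference |
|---|---|---|---|---|
| 10% | 1 | 44.0% | 0.44 × 0.90 = 39.6% | 4.4 points |
| 10% | 0.5 | 44.0% | 0.44 × 0.95 = 41.8% | 2.2 points |
| 10% | 0.2 | 44.0% | 0.44 × 0.98 = 43.1% | 0.9 points |
| 10% | 0 | 44.0% | 44.0% | 0 |
| 15% | 1 | 44.0% | 0.44 × 0.85 = 37.4% | 6.6 points |

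A simulation (n = 250, 200 replicates, 20 logistic imputations) agrees. The printed imputation and the imputation with a non-responder step gave 43.7% and 39.4% (m = 10%, f = 1), 44.1% and 41.9% (m = 10%, f = 0.5), 43.9% and 43.9% (m = 10%, f = 0), and 44.0% and 37.4% (m = 15%, f = 1). Missingness in it was unrelated to response, so it confirms the arithmetic only.

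**AAS7 weeks.** With an assumed weekly AAS7 = 0 rate q of 80–90%, and 5–10% of subject-weeks missing for reasons that should count as non-response, the printed code adds 12 × q × m: from 12 × 0.80 × 0.05 = 0.48 to 12 × 0.90 × 0.10 = 1.08 weeks out of 12.

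**Order of steps.** Section 5.5.1 adds: "Note that the order of multiple imputation and non-responder imputation could be reversed as needed". There the imputed variable is the continuous change score and the zero goes on a separate binary variable, so order matters little. In 5.5.2.2 the imputed variable is the binary response itself, and zeros inserted first become data for the logistic model. Take 80% observed at 44%, 10% drop-outs and 10% lost to termination:
- Non-responder step after PROC MI: 0.80 × 0.44 + 0.10 × 0.44 = 0.352 + 0.044 = 39.6%.
- Zeros first: the model rate is 0.352/0.90 = 39.1%, and the overall rate is also 39.1%.

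**The case against.** The strongest reply is that the governing text is already right and the code is only a sample. SAP 2.14.8 applies the rules of 2.5.3 and 2.6.3 in the final analysis, and 2.6.3 leads back to 2.6.1. The input data set is left blank. Section 5.5.2.2 says that "the secondary analysis will be performed based on the data after the missing data imputation for the intercurrent events has been performed", and 5.5.2.3 opens in nearly the same words. If non-response were set beforehand, PROC MI would see only values meant for MAR. The samples omit other necessary steps too: 5.5.2.3 models the cumulative count without printing the step that sums the imputed weeks.

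Much of this stands. A reader might infer that the analysis does impute every missing value under MAR. The documents do not establish that; they show an incomplete specification that conflicts with 2.6.1 if followed literally. The opening sentence does not cure it, because 5.5.1 opens in the same way and then prints both imputations. The permission to reverse the order appears only in 5.5.1.

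A reader might also infer that all such drop-outs receive the completers' response rate. That goes too far. Retrieved data are used as observed, and Protocol 9.1.1 asks sites to keep early discontinuers on visits until Week 12. The others get draws conditional on IgE, CU index and baseline UAS7 within arm, from a model fitted to everyone observed, including retrieved drop-outs.

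Nor does the departure from the protocol begin in the code. SAP 2.6.1 itself replaces the all-non-responder rule with MAR for study termination.

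**Conclusion.** The point holds as a conflict between the printed code and the SAP's own rule, and it should be corrected. Literal use would overstate UAS7 = 0, DLQI 0-1 and AAS7-free weeks in the drug's favour. For UAS7 = 0 the illustrative ceiling is 4.4 points at 10% missing and 6.6 points at 15%. These are maxima: they require that none of the missingness is termination-related or intermittent and that no data are retrieved. Because the study was terminated early, part of it may well be termination-related, but the documents give no split, and the overstatement falls to 0 if all of it is. For scale, the 95% half-width at 44% is 1.96 × √(0.44 × 0.56/n), or 6.2 points at n = 250 and 4.0 points at n = 600. These endpoints are descriptive, with no inferential methods planned (SAP 2.6.2), so no test result depends on the choice.

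**What to change.** 1. In SAP 5.5.2.2 and 5.5.2.3, add a step by missing reason after PROC MI. It sets the response, or each missing week, to 0 when the value is missing for a reason other than study early termination and is not intermittent. Keep MAR imputation for early-termination and intermittent values, as in step 1 of 2.5.3.
2. State in both subsections that this step follows PROC MI.
3. Do not copy 5.5.1 unedited. The sentence introducing its data step directs non-responder imputation at subjects who stopped because the study was terminated, which reverses its own flag definition. Its flag 0 also turns intermittent missing values into non-response, against step 1 of 2.5.3. Correct both.
4. Separately, SAP Section 4 lists no change to the protocol analyses. Record there that 2.6.1 replaces the all-non-responder rule of Protocol 12.5.1.

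The cost is a few lines of code and text, and possibly slightly lower reported secondary rates.
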